1. INTRODUCTION

Diabetes mellitus (DM) is a disease in which hyperglycemia damages the nerves, kidneys, eyes, and blood vessels over time. The estimated incidence of diabetes in the United States (US) exceeds 1.9 million new cases annually, with an overall prevalence of over 25 million people or 8.3% of the US population (Centers for Disease Control and Prevention, 2011). Type 2 DM (adult onset or non-insulin dependent diabetes) is by far the most common form, occurring in about 95% of subjects diagnosed with diabetes. Diabetic polyneuropathy (DPN) is the most common complication of DM. It develops on a background of long standing, chronic hyperglycemia, associated metabolic derangements, and cardiovascular risk factors.

Although the underlying mechanisms of DPN remain unclear, central features in the development and progression of DPN are neural cell degeneration and decreased nerve blood flow, and are usually associated with both axonal degeneration and demyelination. This results in spontaneous pain (burning pain, electrical or stabbing sensations, deep aching pain, etc.), hyperalgesia, and diminished sensation which is typically worse at night.

Therapies for the treatment of DPN are currently limited to pain relief (tricyclic antidepressants, serotonin norepinephrine reuptake inhibitors, anticonvulsants, opioids, and non-prescription analgesics). There are currently no treatments approved to treat the underlying disease.

Human placenta-derived cells (PDA-002) are characterized as a cellular immune modulating agent that has the potential to induce angiogenesis. PDA-002 is a mesenchymal-like cell population derived from normal, full-term human placental tissue. PDA-002 is culture-expanded as a plastic-adherent, undifferentiated in vitro cell population that expresses the nominal phenotype CD34-, CD10+, CD105+ and CD200+. PDA-002 cells constitutively express moderate levels of human leukocyte antigen (HLA) Class I and undetectable levels of HLA Class II, and they do not express the co-stimulatory molecules CD80 and CD86. PDA-002 is genetically stable, displaying a normal diploid chromosome count, normal karyotype, and exhibits normal senescence after prolonged in vitro culture.

Similar to mesenchymal stromal cells (MSCs) (Aggarwal, 2005; Nauta, 2007) in vitro studies have shown that PDA-002 is capable of immunomodulation. PDA-002 suppresses T-cell proliferation and modulates other cell types involved in immune and inflammatory responses such as T-cell subsets, macrophages and dendritic cells.

In vivo biodistribution and safety studies using mouse models have demonstrated that PDA-002 cells do not proliferate in any tissues and are not associated with any observed toxicity or tumor formation. In a biodistribution study, PDA-002 cells were not detectable at Day 8 in the injected muscle by bioluminescence imaging. The cells did not distribute to other organs, including the lungs. The cells were only detected at the site of injection and in the draining lymph nodes.

The potential beneficial effects of PDA-002 on cellular components of the neurovascular system were tested using a variety of in vitro and in vivo experimental systems. The capacity of PDA-002 to elaborate angiogenic factors, induce endothelial cell survival/proliferation, induce endothelial cell migration, and induce endothelial cell tube formation was assessed.

In rat and mouse models of peripheral neuritis, placental-derived cells have demonstrated dose dependent analgesic effects including pain reduction, suppressed immune cell infiltration, and reduced mechanical sensitivity. The analgesic effects were equivalent to high dose gabapentin.

Additionally, treatment with PDA-002 in mouse hind limb ischemia models demonstrated improvement in blood flow and induced the formation of new collateral blood vessels suggesting angiogenic activity. The effects were comparable to VEGF controls. Please refer to the Investigator's Brochure for details of these studies.

PDA-002 is currently being investigated in 3 independent human studies in subjects with complications of DM. The initial (ongoing) phase 1 open-label, dose escalation study (CCT-PDA-002-DFU-001) is being conducted in 15 subjects with peripheral arterial disease (PAD) with diabetic foot ulceration (DFU) who were refractory to conventional therapy. In this study, intramuscular (IM) injection of either 3×10^6 , 10×10^6 , 30×10^6 , or 100×10^6 PDA-002 cells per treatment on Study Day 1 and Study Day 9 in the affected lower limb was being investigated. Though designed as a safety study, results have demonstrated efficacy in the healing or closure of the index ulcer within 3 months following the initial dose of PDA-002 in 15 subjects to date. Five subjects had complete healing, and 2 subjects had approximately 50% healing of their index ulcer within 3 months. There was a trend for subjects to have increases in their peripheral circulation as measured by the ankle brachial index (ABI). The mean increase in ABI from screening to the start of dosing was 0.003. A clinically significant increase in ABI at 3 months was observed following dosing (0.15). PDA-002 was safe and well tolerated in these subjects who had DFU with PAD.

Study PDA-002-DFU-002 is a Phase 2, randomized, double blind, placebo-controlled, dose range finding study in subjects who have DFU with PAD. Three doses of PDA-002 (3×10^6 , 10×10^6 and 30×10^6 cells) versus placebo will be evaluated in 2:2:1:2 randomization approach, with the lower number of subjects to be allocated to the highest active dose. Approximately 133 subjects will be enrolled. This study is designed as an efficacy and safety study with wound closure of the index ulcer within 3 months after dosing and retaining wound closure for the subsequent 4 weeks as the primary endpoint. The study is ongoing, and the data remain blinded.

Study CCT-PDA-002-DFU-003 is also a Phase 2, randomized, double blind, placebo-controlled dose range finding study in 24 subjects who have DFU with PAD. The study is designed to assess the safety of repeated monthly IM administration of PDA-002, and to generate the data for a clinical proof of mechanism. The study is investigating 3 monthly doses with PDA-002 dose levels (3×10^6 or 30×10^6 PDA-002 cells) on Study Days 1, 29, and 57. Vascular functional parameters as well as potential novel biomarkers will be assessed to predict efficacy and to characterize the treatment response in order to evaluate the pharmacodynamics of treatment with PDA-002. The study is ongoing, and the data remain blinded.

To further evaluate the efficacy and safety of PDA-002, this Phase 2, randomized, double blind, placebo-controlled study will enroll 24 subjects with DPN. The study will employ the same doses and dosing schedule of PDA-002 as the aforementioned proof of mechanism study. The primary endpoint of the study is to assess changes in epidermal nerve fiber density (ENFD), an indicator of small nerve fiber involvement in DPN (Jacobs, 2011). Symptoms of small fiber neuropathy correlate with a decrease in the number, density and length of small nerve fibers in the epidermal layer. Therefore, an increase in ENFD may indicate PDA-002 induced neurogenesis. Additionally, since DPN involves both small myelinated and unmyelinated nerve

fibers (including those responsible for autonomic function) as well as large nerve fibers, various neurophysiological tests are required to identify dysfunction of different nerve populations. Therefore, physiological changes, signs, symptoms, and function related to DPN will be measured as exploratory endpoints.

Please refer to the Investigator's Brochure for detailed information concerning the available pharmacology, toxicology, drug metabolism, clinical studies, and adverse event (AE) profile of PDA-002.

This study will be conducted in compliance with the protocol, Good Clinical Practice (GCP) guidelines, and applicable regulatory requirements.

2. STUDY OBJECTIVES

2.1. Primary Objective

The primary objective of the study is to assess the efficacy of PDA-002 versus placebo in subjects with DPN, based on the change from baseline in epidermal nerve histology at 6 months.

2.2. Secondary Objective

The secondary objective of the study is to assess the safety and tolerability of IM administration of 2 different doses of PDA-002 or placebo in subjects with DPN.

2.3. Exploratory Objectives

The key exploratory objectives of the study are to assess any potential treatment effects of IM administration of 2 different doses of PDA-002 versus placebo in subjects with DPN as measured by changes from baseline in:

- Epidermal nerve histology at 3 months
- Lower limb microvascular oxygenation
- Vascular reactivity
- DPN signs and symptoms
- Motor and sensory nerve conduction and autonomic function
- Health-related quality of life measures
- Vascular, immune, and/or neural and laboratory parameters
- Assessment of the systemic versus local efficacy of PDA-002

3. STUDY ENDPOINTS

3.1. Primary Endpoint

The primary endpoint of the study is to assess the change from baseline in epidermal nerve fiber density (ENFD) at 6 months, an indicator of small nerve fiber involvement, following IM administration of 2 different doses of PDA-002 or placebo in subjects with DPN.

3.2. Secondary Endpoint

The secondary endpoint is to evaluate the safety and tolerability of PDA-002 as measured by the type, frequency, severity, and potential relationship of adverse events to treatment with PDA-002 or placebo.

3.3. Exploratory Endpoints

Exploratory endpoints of the study include measuring changes from baseline in:

- ENFD at 3 months
- Hyperspectral Imaging (HSI) to evaluate lower limb microvasculature oxygenation
- Vascular Reactivity by Laser Doppler Iontophoresis and Nerve Axon Reflex measurements
- Signs/symptoms of DPN as assessed by the 6-item Neuropathy Total Symptom Score (NTSS-6)
- Signs/symptoms of DPN as assessed by the Neurological Impairment Score of the Lower Limb (NIS-LL)
- Signs/symptoms of DPN as assessed by the Utah Early Neuropathy Scale (UENS)
- Motor and sensory nerve conduction and autonomic function as evaluated by electrophysiologic nerve conduction studies
- Quantitative Sudomotor Axon Reflex Testing (QSART)
- Health-Related quality of life (QOL) as measured by the Norfolk QOL-DN
- Vascular, immune, and/or neuronal and laboratory parameters measured in blood and/or epidermal tissues or other biological samples as appropriate
- Patient Global Impression of Change in Neuropathy (PGICN).

4. **OVERALL STUDY DESIGN**

4.1. Study Design

This is a Phase 2, randomized, double-blind, placebo-controlled, dose range finding study in subjects who have DPN. The study will enroll approximately 24 subjects. Subjects will be randomized to receive one of 3 treatments: PDA-002 (3×10^6 cells), PDA-002 (30×10^6 cells), or placebo (vehicle control) in a 1:1:1 randomization approach. Investigational product or placebo will be administered monthly (3 administrations total on Study Days 1, 29, and 57). Subjects will be treated and evaluated as indicated in the Table of Events (Table 1).

Subjects will undergo a Screening Period (up to 28 days in duration) to determine study eligibility and baseline levels of signs and symptoms of DPN will be established. Subjects will then enter a Treatment Period (6 months in duration). During the Treatment Period, subjects will be evaluated on an ongoing basis (at 8 scheduled study visits). Subjects will receive IM injections of IP on Study Days 1, 29, and 57 as fifteen 0.30 mL injections (below the knee and above the ankle) in one lower extremity in a blinded manner. After completing the Treatment Period, subjects will enter the Follow-up Period where they will continue to be evaluated at scheduled study visits over the subsequent months.

An analysis of all study data will occur after the last subject has completed Visit 9 (Month 6) and after the last scheduled study visit. Analyses to be performed can be found in the Statistical Analysis Plan.

The study will be subject to oversight by an independent Data Monitoring Committee (DMC). The DMC will review unblinded efficacy and safety data on an ongoing basis (both scheduled and ad hoc [if needed]) as outlined in the DMC Charter.

4.2. Study Design Rationale

Therapies for the treatment of DPN are currently limited to pain relief (tricyclic antidepressants, serotonin norepinephrine reuptake inhibitors, anticonvulsants, opioids, and non-prescription analgesics). Current treatments do not adequately address the symptoms in a large proportion of subjects with DPN, and there are no approved treatments that target the underlying disease.

One of the major pathophysiologic factors that contributes to DPN is damage to the vasa nervorum or the vascular supply to the nerves involved in DPN. In DPN, vascular damage to the vasa nervorum is induced by glycosylated proteins interacting with receptors to cells that are relevant to the atherosclerotic process, oxidative stress to the vessel wall, and hyperglycemia inducing protein kinase C, which is responsible for increased blood vessel permeability, nitric oxide dysfunction, and increased leukocyte adhesion (Kles, 2006).

Results from the rat hind limb ischemia model show that mesenchymal like stromal cells isolated from human placenta (formulated for IM injection as PDA-002) have potential clinical use in tissue repair through increasing angiogenesis. Furthermore, PDA-002 cells implanted in a mouse model of chronic hind limb ischemia improved blood perfusion and limb functional recovery (see Investigators Brochure).

The assessment of changes in nerve function and microvascular oxygenation in subjects with DPN will be based on a combination of evaluations that will assess nerve histology, DPN signs and symptoms, and tissue perfusion and oxygenation using measurement methods listed in the Table of Events (Table 1).

With regard to route of administration, IM administration of PDA-002 has demonstrated an acceptable safety profile to date. After IM administration in animal models, there was no evidence of distribution to the vascular compartment and PDA-002 cells were detected only at the site of administration and draining lymph nodes. Care will be taken to avoid systemic injection of cells.

The doses selected for this study are based upon the effective doses adjusted for body weight that were administered in the previously described hind limb ischemia (HLI) animal models, as well as the dosing in the Phase 1 study PDA-002-DFU-001. Data on the first 3 dose cohorts of the Phase 1 study in which subjects were administered 3 x 10^6 cells, 10×10^6 cells and 30×10^6 cells on Days 1 and 8 demonstrated that the doses were well tolerated with no reported dose limiting toxicity (DLT). To date based upon the observed safety profile from the Phase 1 study, no new risks have been identified for PDA-002 that would preclude dosing in the Phase 2 studies.

For this study, subjects will be randomized to receive PDA-002 or placebo in one lower extremity in a blinded manner. Although PDA-002 is being administered IM, it is unclear if the therapeutic effect is localized to the area of injection or systemic. In pre-clinical HLI studies, the therapeutic effect of PDA-002 was similar in animals administrated the IM and intravenous (IV) formulation. The mechanism of action of PDA-002 is due to a modulation of the immune system from a pro inflammatory to anti-inflammatory state that facilitates angiogenesis both in the area directly in contact with PDA-002 along with other areas that may be affected by inflammation and ischemia. Since DPN causes a symmetrical dysfunction to the nerves of the lower extremities, assessments of nerve function as well as changes in neurologic signs will be assessed in both legs in order to determine if the therapeutic effect of PDA-002 is local vs. systemic.

The dosing schedule of PDA-002 in this study will be 3 repeated monthly administrations. The schedule is based on the safety of 3 repeat IM doses of PDA-002 demonstrated in animal studies. Please refer to the Investigator's Brochure for detailed information concerning the available pharmacology, toxicology, drug metabolism, clinical studies, and AE profile of PDA-002.

One additional design feature of this study is that while PDA-002 is injected into one leg, both legs are checked for changes in neuropathy signs and symptoms. This will enable determining if the effects of PDA-002 on DPN are limited to the area in which the cells are injected, or the effect is systemic.

Figure 1: Overall Study Design

4.3. Study Duration

Subjects are expected to participate in the study from screening (up to Day -28) to 1 year after the last IP injection.

Subjects will undergo a Screening Period of up to 28 days. During the Screening Period eligibility will be confirmed and baseline assessments will be performed. Subjects will then enter a 6 month Treatment Period consisting of 8 scheduled study visits. During the Treatment Period, IP or placebo will be administered on Study Days 1, 29, and 57, and efficacy and safety evaluations will be performed. Following this, subjects will then enter a Follow-up Period. The Follow up Period will consist of scheduled bi-monthly study visits to continue to assess safety and longer-term efficacy.

4.4. End of Trial

The End of Trial is defined as either the date of the last visit of the last subject to complete the post-treatment follow-up, or the date of receipt of the last data point from the last subject that is required for primary, secondary and/or exploratory analysis, as prespecified in the protocol, whichever is the later date.

5. TABLE OF EVENTS

Table 1:Table of Events

	Screening Period		Treatment Period								Follow-up Period					
	V1	V2	V3	V4	V5	V6	V7	V8	V9	V10	V11	V12	V13			
	Day -28 to Day 0	Day 1 (±3 days)	Day 15 (±3 days)	Day 29 (±3 days)	Day 57 (±3 days)	Day 93 (±7 days)	Day 120 (±3 days)	Day 155 (±3 days)	Day 186 (±7 days)	Day 246 (±7 days)	Day 306 (±7 days)	Day 365 (±7 days)	Day 425 (±7 days)	Early Termin- ation		
Event		Week 1	Week 2	Month 1	Month 2	Month 3	Month 4	Month 5	Month 6	Month 8	Month 10	Month 12	Month 14			
Informed consent	Х	-	-	-	-	-	-	-	-	-	-	-	-	-		
Inclusion/exclusion criteria	Х	-	-	-	-	-	-	-	-	-	-	-	-	-		
Demography/medical and surgical history including duration of diabetes and diabetic peripheral neuropathy	Х	-	-	-	-	-	-	-	-	-	-	-	-	-		
Prior/concomitant medication and procedures	Х	X	Х	Х	Х	Х	Х	Х	Х	Х	Х	Х	Х	Х		
Physical examination including vital signs (height [at Visit 1 only], weight, body temperature, blood pressure, respiration, and pulse ^a	Х	x	-	х	х	X	Х	х	X	X	х	х	Х	Х		
12-Lead electrocardiogram (ECG) ^f	Х	-	-	-	-	-	-	-	-	-	-	-	-	-		
Clinical laboratory testing (serum biochemistry, hematology, coagulation tests urinalysis). Estimated glomerular (eGFR) filtration rate will be calculated (Screening).	Х	х	-	х	Х	-	-	-	х	-	-	-	Х	Х		
Anti-HLA antibodies	Х	Xe	-	Xe	Xe	Х	-	-	-	-	-	-	-	-		
HbA1c testing	Х	-	-	-	-	Х	-	-	Х	-	-	Х	-	Х		
Obtain blood for exploratory biomarker evaluation prior to administration of IP ^b	X	X	-	X	X	X	-	-	X	-	-	-	-	X		

I able 1: I able of Events (Continue)

	Screening Period	Treatment Period									Follow-up Period						
	V1	V2	V3	V4	V5	V6	V 7	V8	V9	V10	V11	V12	V13				
	Day -28 to Day 0	Day 1 (±3 days) Week	Day 15 (±3 days) Week	Day 29 (±3 days) Month	Day 57 (±3 days) Month	Day 93 (±7 days) Month	Day 120 (±3 days) Month	Day 155 (±3 days) Month	Day 186 (±7 days) Month	Day 246 (±7 days) Month	Day 306 (±7 days) Month	Day 365 (±7 days) Month	Day 425 (±7 days) Month	Early Termin- ation			
Event		1	2	1	2	3	4	5	6	8	10	12	14				
Pregnancy test ^c	Х	Х	-	Х	Х	-	-	-	-	-	-	-	-	Х			
Retinal examination	Х	-	-	-	-	-	-	-	Х	-	-	Х	-	Х			
6 Item Neuropathy Total Symptom Score (NTSS-6)	Х	-	-	Х	-	Х	-	-	Х	-	-	Х	-	Х			
Utah Early Neuropathy Scale (UENS)	Х	-	-	Х	-	Х	-	-	Х	-	-	Х	-	Х			
Neuropathy Impairment Score of the Lower Limb (NIS-LL)	Х	-	-	Х	-	Х	-	-	Х	-	-	Х	-	Х			
Electrophysiologic nerve conduction studies	Х	-	-	-	-	-	-	-	Х	-	-	Х	-	Х			
Hyperspectral imaging	Х	-	-	Х	-	Х	-	-	Х	-	-	Х	-	Х			
Quantitative Sudomotor Axon Reflex Testing (QSART)	Х	-	-	-	-	-	-	-	Х	-	-	Х	-	Х			
Skin biopsies	Х	-	-	-	-	Х	-	-	Х	-	-	-	-	-			
Histology of Immune Cells (mast cell)	Х	-	-	-	-	Х	-	-	Х	-	-	-	-	-			
Norfolk Quality of Life Assessment (Norfolk-QOL-DN)	Х	-	-	-	-	Х	-	-	Х	-	-	Х	-	Х			
Patient Global Impression of Change in Neuropathy (PGICN)	X	Х	Х	X	X	-	-	-	Х	-	-	X	-	X			

	Screening Period	Treatment Period				Follow-up Period								
	V1	V2	V3	V4	V5	V6	V7	V8	V9	V10	V11	V12	V13	
	Day -28 to Day 0	Day 1 (±3 days)	Day 15 (±3 days)	Day 29 (±3 days)	Day 57 (±3 days)	Day 93 (±7 days)	Day 120 (±3 days)	Day 155 (±3 days)	Day 186 (±7 days)	Day 246 (±7 days)	Day 306 (±7 days)	Day 365 (±7 days)	Day 425 (±7 days)	Early Termin- ation
Event		Week 1	Week 2	Month 1	Month 2	Month 3	Month 4	Month 5	Month 6	Month 8	Month 10	Month 12	Month 14	
Vascular reactivity measurements- (including Laser Doppler Iontophoresis and Nerve Axon Reflex measurements)	Х	-	-	-	-	Х	-	-	Х	-	-	Х	-	-
Administration of IP	-	Х	-	Х	Х	-	-	-	-	-	-	-	-	-
IP administration monitoring (including visual inspection of injection areas, vital signs, and collection of blood for coagulation tests and tryptase/histamine evaluation before and after IP administration)	-	Х	-	х	х	-	-	-	-	-	-	-	-	-
Assess and record adverse events ^d	Х	Х	Х	Х	Х	Х	Х	Х	Х	Х	Х	Х	X	Х

Table 1:Table of Events (Continued)

Abbreviations: IP=Investigational Product, PBMC=peripheral blood mononuclear cell, RBC=red blood cell, SAE=serious adverse event.

^a Physical exams during the Screening Period and Early Termination will be full physical examinations. At all other assessments, physical examinations should only be directed to evaluate reported adverse events. Assessments for vital signs can be performed within15 minutes for the 1 and 2 hour post dose assessments.

^b Biomarkers assessed at Screening, Visit 2 Day 1 and Visit 4 Day 29, and Visit 5 Day 57 prior to injection of IP. Biomarkers will also be assessed on Day 93 when there is no IP injection. Biomarker samples will include blood immune biomarkers and RBC-lysed PBMC sample for the chip cytometry assay. The chip cytometry assay will only be performed at selected sites.

^c Serum pregnancy testing at Screening and urine pregnancy testing at all other visits of females of childbearing potential. At Visit 2 a urine pregnancy needs to be performed if a serum pregnancy test was not done within 0-72 hours predose. Prior to treatment on Study Days 1, 29, and 57.

^d Adverse events will be followed for 28 days after the last dose of IP. SAEs will be followed until the last study visit.

^e Prior to injection on Days 1, 29 and 57.

^f If performed within 28 days of signing the informed consent it does not need to be repeated.

6. **PROCEDURES**

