6.1. Study Entry/Screening Period (Visit 1)

Visit 1 and Visit 2 can occur up to 28 days apart. All Screening Period procedures should be performed as per Table 1.

Informed Consent/Previous Participation: The initial screening visit will occur up to 28 days prior to the initial administration of IP. Before or at Visit 1, qualified site personnel will explain the study to the subject, answer all of his/her questions, and obtain written informed consent/ Health Insurance Portability and Accountability Act (HIPAA) authorization before performing any study-related procedures. A copy of the signed informed consent will be given to the subject, and the date of the signing of the informed consent will be recorded in the electronic case report form (eCRF) and in the source documents. Previous participation in any other CCT-PDA study will be recorded in the eCRF and in the source documents.

Assessment of Adverse Events: Adverse events (AEs) will be collected from the time the subject signs the informed consent throughout the study. The type, frequency and severity of adverse events and potential relationship to IP will be collected as described in the full study protocol.

Demographics/Medical and Surgical History: Demographics and medical history will be obtained during screening. Demographics will include subject's initials, date of birth, sex, ethnicity, and race. A thorough medical and surgical history including date of diagnosis of DM and DPN, psychiatric conditions, current medical conditions, and any known allergies will be performed.

Prior/Concomitant Medications: All medications taken (including contraception measures) within the last **35 days** should be recorded. All medications that a subject is currently taking will also be recorded from the time the subject signs the informed consent throughout the study.

Physical Examination/Vital Signs: Subjects will undergo a routine physical examination.

Vital signs including height (cm) (Visit 1 only), weight, (kg) body temperature (°C), pulse (beats/minute), respiration (breaths/minute), and resting systolic and diastolic blood pressure (mmHg) will be measured and recorded in the eCRF and in the source documents.

Pregnancy Testing

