6.2. Treatment Period (Visit 2 through Visit 9)

Visit 2 through Visit 9 should occur on the days specified within the allowable variance. All Treatment Period procedures should be performed as per Table 1.

Administration of IP (Visit 2, Visit 4, and Visit 5)

IP will be administered on Study Days 1, 29 and 57. Preparation and administration of IP is discussed in Section 8.2.

IP Administration Information: IP thaw time, start and stop time of injections, and administration interruption/completion will be recorded in the eCRF and in the source documents.

IP Administration Vital Signs: Vital signs including heart rate, respiration, blood pressure, and body temperature will be monitored prior to starting the injections and at 1 and 2 hours after completion of the injections (\pm 15 minutes).

IP Administration Additional Blood Sampling: Blood samples for tryptase and histamine, coagulation assessments (PT/PTT), and exploratory biomarkers will be collected 2 hours before (\pm 15 minutes) IP administration and also at 2 hours after IP administration for tryptase and histamine assessments as indicated in the Table of Events (Table 1).

IP Administration Adverse Event Monitoring: A visual inspection of injection sites will be conducted periodically from the initial injection until 2 hours after the last injection (minimum). Any clinically significant findings will be recorded as AEs in the eCRF and in the source documents.

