6.3. Follow-Up Period

All subjects will be followed for 28 days after the last dose of IP for AE reporting, as well as SAEs that will be followed until the last study visit and made known to the investigator at any time thereafter that are suspected of being related to IP, as described in Section 11.1.

The Follow-up Period will take place from Visit 10 through Visit 13 and include Early Termination. Visits should occur on the day specified ± 3 days or ± 7 days as specified in the Table of Events (Table 1).

All other procedures (as discussed in Section 6.1 and Section 6.2) will be conducted as per the Table of Events (Table 1).

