10.7. Safety Analysis

The safety analyses will be conducted using the Safety Population (all subjects who receive any amount of IP). Adverse events, vital sign measurements, physical examination findings, clinical laboratory test results, injection site assessments, retinal assessment results, ECG interpretations, and concomitant medications and procedures will be tabulated and summarized as appropriate.

Adverse events observed will be classified using the Medical Dictionary for Regulatory Activities (MedDRA) classification system. If clinically significant, any or all laboratory evaluations should be reported as AEs and repeated more frequently, if clinically indicated. The severity of the toxicities will be graded according to the National Cancer Institute (NCI) Common Terminology Criteria for Adverse Events (CTCAE) Version 4.03 whenever possible.

The frequency of AEs will be tabulated by MedDRA system organ class and preferred term. In the by-subject analysis, a subject having the same event more than once will be counted only

once. Adverse events will be summarized by NCI CTCAE grade. Adverse events leading to discontinuation from treatment, events classified as NCI CTCAE Grade 3 or higher, study-drug-related events, and SAEs will be tabulated and listed separately. By-subject listings of all AEs, SAEs, discontinuations due to AEs, and deaths will be provided.

Clinical laboratory data will be summarized. Laboratory data will be graded according to NCI CTCAE Version 4.03 criteria wherever possible. The frequencies of the worst severity grade observed during treatment will be displayed in cross-tabulations by screening status.

Vital signs, ECG, and retinal examination data will be summarized by cross-tabulations presenting normal and abnormal values.

Graphical displays will be provided where useful in the interpretation of results.

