All AEs and SAEs will be recorded by the Investigator from the time the subject signs informed consent until the last study visit and those SAEs made known to the Investigator at any time thereafter that are suspected of being related to IP. AEs and serious adverse events (SAEs) will be recorded on the AE page of the eCRF and in the subject's source documents. All SAEs must be reported to Celgene Drug Safety within 24 hours of the Investigator's knowledge of the event by facsimile, or other appropriate method, using the SAE Report Form, or approved equivalent form.

46

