12.1.2. Mandatory Treatment Discontinuations

Should subjects experience any of the following events, they may not receive additional doses of PDA-002. They should stay on study however, and all scheduled evaluations are to be performed.

- A Grade 3 or higher allergic reaction within 24 hours of PDA-002 administration.
- An episode of symptomatic arterial vasospasm within 24 hours of PDA-002 administration. Examples include acute coronary ischemia and retinal artery spasm.
- An episode of new venous thrombosis within 3 days of PDA-002 administration.

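### The protocol ends non-serious AE collection at two different times (28 days after the last dose, or the last study visit), leaving about 340 days per subject in dispute

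*Combined protocol and SAP*

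**What the plan says.** The protocol gives two rules for when non-serious AE collection stops.

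- **Short window.** Footnote d, attached to the AE row of Table 1 (Section 5), says "Adverse events will be followed for 28 days after the last dose of IP" and then takes SAEs, by contrast, to the last visit. Section 6.3 says "All subjects will be followed for 28 days after the last dose of IP for AE reporting".
- **Long window.** Section 6.1 says "Adverse events (AEs) will be collected from the time the subject signs the informed consent throughout the study". Section 11.1, the dedicated AE section, says "All AEs and SAEs will be recorded by the Investigator from the time the subject signs informed consent until the last study visit".

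SAEs are treated alike everywhere: footnote d and Sections 6.3, 11.1 and 11.5 all run them to the last visit.

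Four other places bear on the point:

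- Section 3.2 makes safety and tolerability the secondary endpoint, "as measured by the type, frequency, severity, and potential relationship of adverse events to treatment with PDA-002 or placebo".
- Section 10.7 says "The frequency of AEs will be tabulated by MedDRA system organ class and preferred term" but names no time window. Section 6.5 mentions treatment-emergent events without defining them.
- Section 12.1.2 says of subjects who must stop dosing: "They should stay on study however, and all scheduled evaluations are to be performed".
- Sections 10.1 and 10.6 refer to a separate SAP, which is not among the documents available.

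**The concern.** A site cannot follow both rules. One that works from footnote d or Section 6.3 stops entering non-serious AEs about four weeks after the last dose. One that works from Section 6.1 or 11.1 continues for roughly another eleven months. Three consequences follow.

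1. **Incomplete or uneven data on the secondary endpoint.** Tables of non-serious AEs after about Day 85 may be incomplete, or may differ by site. Site differences are a risk and not a documented fact; training and monitoring may reduce it. Table 1 places both post-baseline retinal examinations (V9 and V12) and the laboratory panels at V9 and V13 in the disputed span. Section 11.3 makes certain laboratory abnormalities AEs, but under the short rule a non-serious one found at those visits would not be recorded.
2. **Observation time tied to dosing.** Under the short window a subject who stops dosing early also leaves AE observation early, although Section 12.1.2 keeps some such subjects on study with every evaluation. Their AE counts would then rest on less follow-up than those of fully dosed subjects.
3. **A narrow case for the DMC.** Sections 6.5.1 and 12.1.1 make a new malignancy a trigger with no time limit. One found after the cut-off and judged non-serious might never be entered as an AE.

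A later SAP could define an analysis window, but it could not restore events that were never recorded.

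**Working it through.** **Inputs**

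- Dosing: Section 6.2, "IP will be administered on Study Days 1, 29 and 57". The Day 57 visit has a window of ±3 days (Table 1).
- Last scheduled visit: V13, Day 425 ±7 days (Table 1).
- Short rule: last dose + 28 days. Long rule: last visit.
- Screening: up to 28 days. Planned enrolment: 24 subjects.

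**Check of the plan's own figure.** Section 4.3 puts participation at one year after the last injection. From Table 1, 425 − 57 = 368 days, which agrees within the visit window.

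**Disputed span after three doses**

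- Short rule ends: 57 + 28 = Day 85. Long rule ends: Day 425.
- Span: 425 − 85 = **340 days**.
- With visit windows the last dose falls on Day 54 to 60, so the cut-off is Day 82 to 88, and V13 falls on Day 418 to 432. The span is 418 − 88 = 330 to 432 − 82 = 350 days.
- If follow-up ended exactly 365 days after Day 57 (Day 422): 422 − 85 = 337 days.
- Share of time from Day 1: 340 / (425 − 1) = 80.2%.
- Share of time from consent, with a full 28-day screening: 340 / (425 + 28) = 75.1%.

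**Visits affected.** V6 (Day 93 ±7, so Day 86 to 100) can fall before the latest cut-off of Day 88 and is needed to collect events from the short window, so it is not counted. V7 to V13 lie clearly beyond the cut-off: 7 of the 12 post-screening visits V2 to V13.

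**AE observation by number of doses, for a subject followed to V13**

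| Last dose | Short-rule cut-off | AE days from Day 1, short rule | AE days from Day 1, long rule | Disputed days |
|---|---|---|---|---|
| Day 1 | Day 29 | 28 | 424 | 396 |
| Day 29 | Day 57 | 56 | 424 | 368 |
| Day 57 | Day 85 | 84 | 424 | 340 |

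**Whole trial, all 24 subjects fully dosed and followed**

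- Short rule: 24 × 84 = 2,016 subject-days.
- Long rule: 24 × 424 = 10,176 subject-days.
- Difference: 24 × 340 = 8,160 subject-days.

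**Illustration only.** Assume a constant background event rate, which the documents do not give. An event with incidence p by Day 85 then reaches 1 − (1 − p)^(424/84) by Day 425. For p = 5%, 10% and 20% this gives 22.8%, 41.2% and 67.6%. It shows how far the choice of window could move a reported frequency; it does not predict this trial's results.

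**Can the wording be reconciled?** One could read footnote d as limiting only the follow-up of events already recorded. That fails, because Section 6.3 applies the same 28 days to reporting and the footnote qualifies the Table 1 row for assessing and recording AEs.

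**The case against.** The strongest reply is that the text leans towards the long window, so the defect amounts to a stray limit in one footnote and one sentence. The evidence for this is real:

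- The AE row of Table 1 is marked at every visit from V1 to V13 and at early termination.
- Footnote a directs physical examinations, outside screening and early termination, to reported AEs, and Table 1 schedules them at every visit from V6 to V13.
- Section 11.1 also says that subjects are monitored for AEs during the study.
- Section 6.3 closes by pointing to Section 11.1, which holds the longer rule.
- The requirement in Section 12.1.2 to perform all evaluations fits the long window as well.

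This helps choose the remedy but does not remove the conflict. The later marks in the AE row can be read as SAEs only, because footnote d qualifies that row. The pointer in Section 6.3 may cover only its SAE clause. No passage gives one rule precedence.

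Other objections stand in part. The 340 days describe what the short rule would leave out, not a documented loss. The incidence figures rest on an assumed rate. The malignancy case needs an event judged non-serious despite the important-medical-event criterion in Section 11.2.1, and the DMC trigger is not expressly tied to an AE form entry. Either window would apply to all three arms alike. Splitting the AE tables by period is good practice but is not needed to remove the contradiction.

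**Conclusion.** The concern holds. Two passages stop non-serious AE collection 28 days after the last dose, two continue it to the end of the study, and nothing in the protocol decides between them. This is an internal contradiction between stated rules on the data for the secondary endpoint, and it should be corrected.

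The nominal size is 340 days per subject. That figure assumes three doses on schedule and attendance at V13; it is longer if dosing stops early and the subject stays on study. How many events would be lost cannot be known from the documents, because that depends on which passage each site follows. The harm is confined to late non-serious AEs.

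**What to change.** Bring footnote d and Sections 6.1, 6.3 and 11.1 to a single window. The simplest route is to amend footnote d and Section 6.3 to match Sections 6.1 and 11.1, since the visits to V13 already take place. Footnote d could state that every AE, serious or not, is recorded from consent to the final visit, with a reference to Section 11.1.

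In Section 10.7, state the AE window. Tabulate events up to 28 days after the last dose separately from later events, with subject-days of observation for each arm.

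A short window stated consistently throughout would also end the contradiction, but AE observation time would still vary with the number of doses received.

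The cost is wording changes in three places (footnote d, Section 6.3 and Section 10.7) and slightly more non-serious AE data entry at V7 to V13. No visit or procedure is added.
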